8.2 Secondary Endpoints

8.2.1 Transfusion-independence for red blood cells and/or platelets: ability to maintain a hemoglobin >8gm/dl and a platelet count > 20 000/ μ L without the need for transfusions for a period of 6 weeks regardless of subsequent events.

8.2.2 Overall survival which is defined as the time elapsed between time of treatment and death and will be compared between responders and non-responders. Any such comparison may be biased and needs to be interpreted cautiously.

8.2.3 Life threatening toxicity. Subjects who do not complete the treatment course because of toxicity or voluntary withdrawal will be included in analyses.

8.2.4 Overall survival and transformation-free survival, which is defined as the time elapsed (reported at 3 month intervals for the first four years, then yearly thereafter) between time of treatment, and bone marrow morphologic evidence for progression (as determined by FAB criteria), development of acute leukemia, or death will be compared between responders and non-responders. Any such comparison may be biased and needs to be interpreted cautiously.

8.2.5 Response duration will be determined as the interval between time of onset of response as outlined above, and the time of relapse or loss of response characteristic (reported at 3 month intervals for the first four years, then yearly thereafter).

8.2.6 Affects of the addition of cyclosporine. Subjects who relapse after responding to Campath will be given CsA to determine if CsA will be beneficial under these circumstances. For this protocol, CsA is investigational, subjects will be followed, data will be collected and analyzed as secondary endpoints. The number of subjects who will receive CsA cannot be predicted since it will depend on the initial response to Campath which is unknown.

Response proportion, response duration, overall survival, and transformation free survival will be determined and compared within the FAB sub-groups and International Prognostic Scoring System categories of MDS and with the results of previous studies at the NIH using h-ATG alone or CsA alone to treat the cytopenia of MDS.

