One such novel therapy, alemtuzumab (Campath®) is a humanized IgG1 monoclonal antibody directed against the CD52 protein, which is highly expressed on all lymphoid cells and monocytes. Alemtuzumab (Campath®) produces profound and persistent lymphopenia, affecting predominantly the CD4+ T cell subset. This property has made it attractive in the treatment of a wide range of diseases including rheumatoid arthritis, multiple sclerosis, ocular inflammatory disease, lymphoid malignancies, organ allograft rejection, and in conditioning regimens in stem cell transplantation to prevent graft failure and graft-versus-host disease.

We therefore propose a non-randomized, off label, pilot, Phase I/II study of alemtuzumab (Campath®) in MDS patients who are likely to respond to immunosuppression.

Primary endpoints will be changes in peripheral blood counts (platelets, absolute neutrophil count, reticulocyte count, hemoglobin). Secondary endpoints (in transfusion-dependent patients) include improvement in the transfusion requirements (measured as decrease in the number of transfusion administered on "as needed basis"), duration of response, late effects of treatment, relapse and survival.

TABLE OF CONTENTS

- 1.0 OBJECTIVES
- 2.0 BACKGROUND
- 3.0 STUDY DESIGN
- 4.0 ELIGIBILITY ASSESSMENT
- 5.0 TREATMENT PLAN
- 6.0 CLINICAL EVALUATION
- 7.0 LABORATORY RESEARCH STUDIES
- 8.0 BIOSTATISTICAL CONSIDERATIONS
- 9.0 DATA AND SAFETY MONITORING
- 10.0 HUMAN SUBJECTS PROTECTION
- 11.0 PHARMACEUTICALS

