APPENDIX A

APPENDIX B

1.0 OBJECTIVES

The primary objective of this clinical protocol is to assess the safety and efficacy of the genetically engineered humanized anti-CD52 monoclonal antibody, alemtuzumab (Campath®) on blood counts and transfusion requirements in patients with myelodysplastic syndromes.

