4.1 Inclusion Criteria

4.1.1 MDS with WHO classification of RA, RARS, RCMD-RS, and RCMD and RAEB-1

4.1.2 Anemia requiring transfusion support with at least one unit of packed red blood cells per month for greater than or equal to 2 months

OR

Anemia (hemoglobin <9 or a reticulocyte count <60,000)

OR

thrombocytopenia (platelet count less than 50000/ μ L)

OR

neutropenia (absolute neutrophil count less than 500/ μ L).

- 4.1.3 Off all other treatments for MDS (except filgrastim [G-CSF]), erythropoietin, and transfusion support and related medications) for at least four weeks. Filgrastim (G-CSF) can be used before, during and after the protocol treatment for patients with documented neutropenia (<500/Ul) as long as they meet the criteria for anemia and/or thrombocytopenia as stated above.
- 4.1.4 Ages 18-72 (inclusive)

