5.4 Supportive Treatment

- Transfusal support care (e.g., blood and platelets) as clinically indicated.
- Growth factors if deemed necessary by the investigator

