If. Disease transformation: Transformation to AML (30% or more blasts).

Ig. Survival and progression-free survival

II. Cytogenetic response

IIa Major: No detectable cytogenetic abnormality, if preexisting abnormality was present.

IIb Minor: 50% or more reduction in abnormal metaphases.

Requires 20 analyzable metaphases using conventional cytogenetic techniques. Fluorescent in situ hybridization may be used as a supplement to follow a specifically defined cytogenetic abnormality.

III. Hematologic Improvement (HI)

Improvements must last at least 2 months in the absence of ongoing cytotoxic therapy.† Hematologic improvement should be described by the number of individual, positively affected cell lines (eg, HI-E; HI-E 1 HI-N; HI-E 1 HI-P 1 HI-N).

IIIa. Erythroid response (HI-E)

- *Major response:* For patients with pretreatment hemoglobin less than 11 g/dL, greater than 2 g/dL increase in hemoglobin; for RBC transfusion-dependent patients transfusion independence.
- *Minor response:* For patients with pretreatment hemoglobin less than 11 g/dL, 1 to 2 g/dL increase in hemoglobin; for RBC transfusion-dependent patients, 50% decrease in transfusion requirements.

IIIb. Platelet response (HI-P)

- *Major response:* For patients with a pretreatment platelet count less than 100 000/mm³, an absolute increase of 30 000/mm³ or more; for platelet transfusion-dependent patients, stabilization of platelet counts and platelet transfusion independence.
- *Minor response:* For patients with a pretreatment platelet count less than 100 000/mm³, a 50% or more increase in platelet count with a net increase greater than 10,000/mm³ but less than 30,000/mm³.

IIIc. Neutrophil response (HI-N)

- *Major response:* For absolute neutrophil count (ANC) less than 1500/mm³ before therapy, at least a 100% increase, or an absolute increase of more than 500/mm³, whichever is greater.
- *Minor response:* For ANC less than 1500/mm³ before therapy, ANC increase of at least 100%, but absolute increase less than 500/mm³.

IIId. Progression/relapse after HI:

One or more of the following: a 50% or greater decrement from maximum response levels in granulocytes or platelets, a reduction in hemoglobin concentration by at least 2 g/dL, or transfusion dependence.§

For a designated response (CR, PR, HI), all relevant response criteria must be noted on at least 2 successive determinations at least 1 week apart after an appropriate period following therapy (eg, 1 month or longer).

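### The 6-week transfusion-independence endpoint in 8.2.1 has no denominator, assessment window or baseline comparison, so it can credit subjects whose transfusion need has not changed

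*Combined protocol and SAP*

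**What the plan says.** Section 8.2.1 defines transfusion independence for red cells and/or platelets as "ability to maintain a hemoglobin >8gm/dl and a platelet count > 20 000"/µL, "without the need for transfusions for a period of 6 weeks regardless of subsequent events". It names no population, no start or end of assessment and no comparison with the period before treatment.

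Entry under 4.1.2 is by any one of several routes joined by OR. The transfusion route is "Anemia requiring transfusion support with at least one unit of packed red blood cells per month for greater than or equal to 2 months". Another is "Anemia (hemoglobin <9 or a reticulocyte count <60,000"), and platelets below 50,000/µL or neutrophils below 500/µL also suffice. Transfusion dependence is not separately defined.

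Three other places bear on the point. The synopsis limits the population and measures a decrease in transfusions: "Secondary endpoints (in transfusion-dependent patients) include improvement in the transfusion requirements". The hematologic improvement criteria in Appendix B state "Improvements must last at least 2 months in the absence of ongoing cytotoxic therapy". Section 1.0 makes the effect "on blood counts and transfusion requirements in patients with myelodysplastic syndromes" part of the primary objective.

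**The concern.** A measure of transfusion independence should separate subjects whose need has fallen from those whose need is unchanged. Section 8.2.1 can fail to do so in two ways.

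- An untransfused subject can meet it at baseline, because its count floors lie below the hemoglobin and platelet entry limits.
- A subject transfused about monthly can pass through a single 6-week gap by ordinary variation in timing, and a later return to transfusion does not reverse the credit.

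The trial is non-randomized, so no concurrent group shows how often such gaps arise without the drug. The reported independence rate could overstate benefit, most of all among subjects with the least need at entry.

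**Working it through.** **The plan's own figures.** The plan gives no figure for 8.2.1. Its only sample-size calculation (8.3; continue if more than 6 of 19 respond, succeed if more than 16 of 39 respond) reproduces exactly: type I error 0.0455 at 30% and power 0.8036 at 50%. It uses response under 8.1.

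**Step 1: subjects who qualify before dosing.** This needs no model. Take a never-transfused subject with hemoglobin 8.5 g/dL and platelets 30,000/µL, both stable for 6 weeks.

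- Entry under 4.1.2: 8.5 < 9 and 30,000 < 50,000, so eligible.
- Section 8.2.1: 8.5 > 8, 30,000 > 20,000 and no transfusion, so met on day 0.

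The same holds for an untransfused subject entered on neutropenia alone with counts above both floors.

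**Step 2: the window against the usual gap.** One transfusion a month means an average gap of 52.18/12 = 4.35 weeks. The 6-week requirement is 6/4.35 = 1.38 times that. Two months is 8.7 weeks, twice the average gap.

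**Step 3: chance of a qualifying gap with no change in need.** The documents give no distribution of gaps, so this is an assumption shown over a range. Gaps are gamma distributed with constant mean m and coefficient of variation CV (shape 1/CV², scale m·CV²). A success is any transfusion-free gap of at least the required length inside the window. The hemoglobin and platelet floors are ignored, so each figure is an upper bound for its timing assumption. Results are from simulation, 40,000 subjects per cell.

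| Transfusions per month | CV | 6-week gap by 3 months | 6-week gap by 6 months | 2-month gap by 6 months |
|---|---|---|---|---|
| 1 | 0 (regular) | 0% | 0% | 0% |
| 1 | 0.2 | 7% | 17% | 0% |
| 1 | 0.3 | 20% | 44% | 1.4% |
| 1 | 0.5 | 39% | 73% | 18% |
| 1 | 1 (random) | 64% | 92% | 60% |
| 2 | up to 0.3 | 0% | 0% | 0% |
| 2 | 0.5 | 2% | 4% | 0.1% |
| 2 | 1 (random) | 27% | 54% | 16% |

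**Step 4: a case that meets 4.1.2 literally.** Suppose exactly one unit is given in every calendar month, on a uniformly random day. For two successive months, the gap reaches 1.38 months with probability (1 − 0.38)²/2 = 0.19. Three months contain two such pairs, giving about 2 × 0.19 = 0.38. Simulation gives 38% by 3 months and 74% by 6 months. A gap of 2 months cannot occur under this pattern, so lengthening the period to 2 months removes these false credits completely.

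**The case against.** Much of the case on the other side stands.

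- *The endpoint is more than a transfusion-free spell.* The count floors must also be maintained. The documents set no transfusion trigger (support is given as "blood and platelets) as clinically indicated"), so their effect cannot be computed and the percentages remain upper bounds.
- *A reader might infer that unchanged subjects will often be scored as successes.* The documents do not support that. Frequency turns on irregularity of timing, which is not given. The chance is zero for regular monthly transfusion and close to zero at two a month unless timing is irregular. Section 4.1.2 sets one unit a month as a minimum, not an average.
- *A reader might extend the argument to two units every two months, or to 12 months and the 5 years of visits.* Such a schedule normally leaves a month without a unit, so read literally it does not meet the transfusion route. Sections 5.2.1 and 8.6 take non-responders off study, so unchanged subjects do not generally accumulate years of chances. The figures therefore stop at 6 months.
- *A baseline comparison exists elsewhere.* The synopsis restricts the population and looks for a decrease, and 8.1 has a 50% decrease criterion. This is true, but 8.2.1 carries over neither, so as written it conflicts with the synopsis.
- *Six weeks against two months is a matter of preference.* Appendix B's duration does govern hematologic improvement and not 8.2.1 directly, and a first-occurrence measure is legitimate if labelled as such. But 8.2.1 gives no reason for a shorter period than the plan's own response standard, and step 4 shows that the difference matters at the entry minimum.

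**Conclusion.** The point holds as a defect of definition in a secondary endpoint, and the sponsor should correct it. What is certain from the text is that 8.2.1 lacks a denominator, a window and a baseline comparison, and that some eligible untransfused subjects can meet it before treatment.

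What depends on assumptions is how often transfused subjects with unchanged need would qualify. At one transfusion a month the chance is 0% if strictly regular, about 7-64% by 3 months and 17-92% by 6 months for CV 0.2 to 1. All are upper bounds, and they are lower with more frequent transfusion.

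A reader might infer that the go/no-go decision is compromised. It is not, on the text: no test, sample size or stopping rule uses 8.2.1. The exception would arise if its definition were applied to the term transfusion independence in 8.1, which leaves that term undefined.

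**What to change.** In 8.2.1:

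1. Restrict the red-cell denominator to subjects who entered by the transfusion route of 4.1.2, and the platelet denominator to those platelet-transfusion-dependent at baseline. State how that is determined. This brings 8.2.1 into line with the synopsis.
2. Require a transfusion-free period of at least 2 months, as Appendix B does, inside a fixed window tied to the 3-, 6- or 12-month landmark.
3. Report units transfused in matched windows before and after treatment. The longer period is not enough alone: under random timing at one transfusion a month it still leaves about 60% by 6 months.
4. Keep the 6-week version only as a supplementary first-occurrence measure, labelled as such.
5. State whether this definition applies to transfusion independence in 8.1.

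The cost is wording plus the dates of units in the months before treatment, which checking 4.1.2 already requires. The denominator will be smaller and the reported rate lower. Section 10.4 places the study in data analysis only from January 2017, so the change should be declared as made after data collection, with both versions shown.

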5.2.2 Subjects who have responded to Campath-1H and then relapse

Subjects who relapse after initial response to Campath-1H measured at 3 months (see section 6.4) will have CsA added to the protocol therapy regimen unless otherwise contraindicated. CsA will be started at 10 mg/kg/d by mouth in divided doses q12 hr. Dosing will be based on ideal body weight and will be adjusted to maintain a target level of 200 – 400 ng/ml. If the blood counts improve, the CsA will be continued and tapered off gradually and the subject will continue to be followed on study. The CsA may be continued for 2-3 months or longer at the discretion of the PI to determine if immunosuppression with CsA will further improve the blood counts.

- If there is no improvement, the CsA will be discontinued and the subject will go off study.
- If further relapses occur while the subject is on therapeutic CsA (blood level of 200-400 ng.ml), then the subject will go off study.

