6.3 Post Treatment Monitoring Discharge Home Through 3 Months

After completing treatment, subjects will be followed by their home physician or at the Clinical Center and have blood work done as detailed below. Progress notes and laboratory results from home physicians will be faxed to the Research nurse, [name], [contact]. Subjects must be evaluated at the Clinical Center at the 1 month (+/- 7 days) and 3 month (\pm 7 days) time points

- Physical examination
- Complete blood counts with differential (weekly +/- 3 days)
- DAT (direct antiglobulin test) (months 1 and 3 +/- 2 weeks)
- Type and screen (at 1 month and 3 months only +/- 2 weeks or if clinically indicated)
- Acute care, mineral, hepatic and other panel (Home MDs: electrolytes, transaminases, urea nitrogen (BUN), serum creatinine, total bilirubin) (weekly +/- 3 days)
- EBV and CMV PCR in the blood (weekly +/- 3 days) for the first month, then every other week +/- 3 days) in the second month, and then monthly (+/- 2 weeks) starting in month 3
- Reticulocyte count (at 1 and 3 months only, Home MDs only if available)
- ECHO (at 3 months only +/- 2 weeks)
- Serum troponin-I (at 3 months only +/- 2 weeks)
- Thyroid function tests (at 3 months only +/- 2 weeks)
- Flow cytometry of the peripheral blood for GPI-cells (at 3 months only +/- 2 weeks)

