6.4 Post Treatment Monitoring 4 Months to 6 Months

After the 3 month visit, subjects will be followed by their home physician or at the Clinical Center and have blood work done as detailed below. Progress notes and laboratory results from home physicians will be faxed to the Research nurse, [name], [contact]. Subjects must be evaluated at the Clinical Center at the 6 month (\pm 7 days) time point

- Physical examination
- Complete blood counts with differential (every other week +/- 3 days)
- DAT (direct antiglobulin test) (6 months +/- 1 month)
- Type and screen (at 6 months only +/- 2 weeks)
- Acute care, mineral, hepatic and other panel (every other week +/- 3 days) (Home MDs: electrolytes, transaminases, urea nitrogen (BUN), serum creatinine, total bilirubin)
- EBV and CMV PCR in the blood monthly (+/- 2 weeks) to 6 months.
- Reticulocyte count (at 6 months only, Home MDs only if available)
- Thyroid function tests (at 6 months only +/- 1 month)

- Bone marrow biopsy and aspiration with cytogenetics (6 months (+/- 1 month only)
- Flow cytometry of the peripheral blood for GPI-cells (6 months (+/- 1 month only)
- If Cyclosporine (CsA) is added: CsA levels will be monitored every week (+/- 3 days) for the first month and then every other week (+/- 3 days) for the remainder of the treatment period. Less frequent monitoring may occur if CsA drug level is therapeutic and steady. Dosing will be adjusted to maintain blood level of 200 – 400 ng/ml. More frequent drug serum levels may be obtained as needed to achieve constant therapeutic levels.

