8.0 BIOSTATISTICAL CONSIDERATIONS

8.1 Primary Endpoint

The primary endpoint is hematologic response measured at 3 months after first dose alemtuzumab (Campath®) sustained on at least two serial measurements at least one week apart at landmark time points (3, 6 and 12 months) will be defined using standard hematologic and cytogenetic response criteria for MDS (See Appendix B for detailed description)⁷⁷.

Complete response: Normalization of all affected cell lines (Hemoglobin, Reticulocyte count, Platelets, ANC)

Partial response: At least one minor response

1. Hemoglobin Response

Major response: For subjects with pretreatment hemoglobin less than 11 g/dL, greater than 2 g/dL increase in hemoglobin; for RBC transfusion-dependent subjects, transfusion independence or an absolute reticulocyte count to $\geq 60,000/\mu\text{L}$ of blood in transfusion-dependent patients.

Minor response: For subjects with pretreatment hemoglobin less than 11 g/dL, 1 to 2 g/dL increase in hemoglobin; for RBC transfusion-dependent patients, 50% decrease in transfusion requirements.

2. Platelet response

Major response: For subjects with a pretreatment platelet count less than $100,000/\text{mm}^3$, an absolute increase of $30,000/\text{mm}^3$ or more; for platelet transfusion-dependent subjects, stabilization of platelet counts and platelet transfusion independence.

Minor response: For subjects with a pretreatment platelet count less than 100,000/mm³, a 50% or more increase in platelet count with a net increase greater than 10,000/mm³ but less than 30,000/mm³.

3. ANC response

Major response: For absolute neutrophil count (ANC) less than 1500/mm³ before therapy, at least a 100% increase, or an absolute increase of more than 500/mm³ whichever is greater.

Minor response: For ANC less than 1500/mm³ before therapy, ANC increase of at least 100%, but absolute increase less than 500/mm³.

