8.3 Sample Size

Because the efficacy of this treatment is almost completely unknown, we would like to reject the treatment as quickly as possible with a small number of subjects if the treatment is not effective.

A response probability of 30% or less would warrant terminating the treatment on this subject population, and we hypothesize that the actual response probability using this treatment would reach 50% or more.

Let p be the probability of complete or partial response at 3 months. Our sample size is determined by testing the null hypothesis $H_0: p \leq 30\%$ versus the alternative $H_1: p \geq 50\%$ at 0.05 significance level and 0.80 of the power. We determine the sample size using the Two-Stage Minimax Design outlined in Table 1 of Simon (1989)⁷⁵ This design is selected because it requires a smaller total number of subjects ($n=39$) than the Simon's Two-Stage Optimal Design ($n=46$). At the first stage, 19 subjects will be accrued and the null hypothesis will be accepted (i.e., the treatment will be terminated) if 6 or less subjects respond to the treatment at 3 months. If 7 or more subjects respond to the treatment at 3 months in the first stage, then an additional 20 subjects will be accrued, bringing the total number of subjects to $n=39$. The null hypothesis of $p \leq 30\%$ will be accepted if the total number of complete and partial responders at 3 months is 16 or less.

An additional 39 subjects will be enrolled to allow for statistically valid subgroup comparisons of secondary endpoints such as response to cyclosporine in subjects who relapse within six months of treatment.

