APPENDIX B :INTERNATIONAL WORKING GROUP PROPOSED STANDARDIZED CRITERIA FOR RESPONSE IN MDS⁷⁷

I. Altering Disease Natural History

Ia. Complete remission (CR)

05-H-0206

[name]

April 26, 2018

Peripheral blood evaluation (absolute values must last at least 2 months)†:

- Hemoglobin greater than 11 g/dL (untransfused, patient not on erythropoietin)
- Neutrophils 1500/mm³ or more (not on a myeloid growth factor)
- Platelets 100 000/mm³ or more (not on a thrombopoietic agent)
- Blasts, 0%
- No dysplasia*

Bone marrow evaluation: Repeat bone marrow showing less than 5% myeloblasts with normal maturation of all cell lines, with no evidence for dysplasia.* When erythroid precursors constitute less than 50% of bone marrow nucleated cells, the percentage of blasts is based on all nucleated cells; when there are 50% or more erythroid cells, the percentage blasts should be based on the nonerythroid cells.

Ib. Partial remission (PR)

All of the CR criteria (if abnormal before treatment) (absolute values must last at least 2 months); except:
Bone marrow evaluation: Blasts decreased by 50% or more over pretreatment, or a less advanced MDS FAB classification than pretreatment. Cellularity and morphology are not relevant.

Ic. Stable disease: Failure to achieve at least a PR, but with no evidence of progression for at least 2 months.

Id. Failure: Death during treatment or disease progression characterized by worsening of cytopenias, increase in the percentage bone marrow blasts, or progression to an MDS FAB subtype more advanced than pretreatment.

Ie. Relapse after CR or PR: one or more of the following:

- a) Return to pretreatment bone marrow blast percentage.
- b) Decrement of 50% or greater from maximum remission/response levels in granulocytes or platelets.
- c) Reduction in hemoglobin concentration by at least 2 g/dL or transfusion dependence.§
6. Disease progression
 - a) For patients with less than 5% blasts: a 50% or more increase in blasts to more than 5% blasts.
 - b) For patients with 5% to 10% blasts: a 50% or more increase to more than 10% blasts.
 - c) For patients with 10% to 20% blasts: a 50% or more increase to more than 20% blasts.
 - d) For patients with 20% to 30% blasts: a 50% or more increase to more than 30% blasts.
 - e) One or more of the following: 50% or greater decrement from maximum remission/response levels in granulocytes or platelets, reduction in hemoglobin concentration by at least 2 g/dL, or transfusion dependence.§

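### Survival is compared by response from the day of treatment, although response is not known until 3 months or later; a landmark analysis removes the built-in advantage to responders

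*Combined protocol and SAP*

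**What the plan says.** - **Time origin.** Sections 8.2.2 and 8.2.4 measure overall survival and transformation-free survival from treatment. Each is an outcome that "will be compared between responders and non-responders. Any such comparison may be biased and needs to be interpreted cautiously".
- **When response is known.** Section 8.1 reads the primary response 3 months after the first dose and requires it to be "sustained on at least two serial measurements at least one week apart at landmark time points (3, 6 and 12 months"). Section 8.3 uses the same time: "Let p be the probability of complete or partial response at 3 months". So does section 5.2.2: "Subjects who relapse after initial response to Campath-1H measured at 3 months". The landmark times in 8.1 are response assessments, not a start point for survival.
- **Duration.** Appendix B, to which 8.1 refers for detail, adds for hematologic improvement: "Improvements must last at least 2 months in the absence of ongoing cytotoxic therapy".
- **Early deaths.** No section says which group holds a subject who dies before the 3-month assessment. Section 8.3 counts responders among all accrued subjects. Appendix B has an entry "Failure: Death during treatment or disease progression characterized by worsening of cytopenias".
- **Methods.** Section 8.4 names Kaplan-Meier, Cox regression and competing-risk models. It names neither a landmark analysis nor response as a time-dependent covariate.
- **After non-response.** Under 5.2.1 and 8.6, non-responders leave the study with laboratory monitoring specified to 6 months off drug. Section 8.2.4 nevertheless plans survival reporting over several years.

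**The concern.** The grouping variable is settled after the survival clock has started. A responder must have lived to the 3-month assessment and through its confirmation, so survival over that period is 100% in that group by definition. If every death in the period goes to the other group, the two curves separate before response could have had any effect. This is immortal-time bias.

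The caution in 8.2 discloses that the comparison may mislead, but it neither names this source nor removes it. Prognostic differences between responders and non-responders cannot be removed in a single-arm study. This component can. At stake is a published impression that response to alemtuzumab prolongs survival. The comparison is secondary and drives no decision within the trial.

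**Working it through.** **The plan's own figures.** The plan gives no effect size, test or power for the survival comparison. Its one computed design, the two-stage minimax design in 8.3, reproduces: stopping at 6 or fewer of 19 and accepting the null at 16 or fewer of 39 gives type I error 0.0455 at 30% response and power 0.8036 at 50%.

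**Inputs from the documents.** Response rates of 30% and 50% and sample sizes of 39 and 39 + 39 = 78 (8.3). Visits to 5 years, taken as 60 months (6.5). The only early-mortality figure in MDS is 7/38 = 18.4% within 3 months on h-ATG/CsA (2.10).

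**Assumptions, not in the plan.** Early deaths count as non-responders. Early mortality d is 2%, 5%, 10% or 18.4%. Deaths are uniform over months 0 to 3, then the hazard is 0.02 per month in both groups. Follow-up to 60 months is complete. The test is a two-sided 5% log-rank test. Response is unrelated to survival throughout.

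**Step 1: closed form.** Let r be the response share among subjects alive at 3 months. Three-month survival is 1 in responders. In non-responders it is

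(1 − d)(1 − r) / [d + (1 − d)(1 − r)].

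With r = 0.5:
- d = 0.05: 0.475/0.525 = 0.905
- d = 0.10: 0.450/0.550 = 0.818
- d = 7/38: 0.408/0.592 = 0.689

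The true difference is zero in each case.

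**Step 2: simulation from time of treatment, status fixed at month 3** (10,000 trials per setting; hazard ratio, HR, is responders versus non-responders).

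| Early death | HR, n=78, 50% resp. | Rejection | HR, n=78, 30% resp. | Rejection | Rejection, n=39, 50% | Rejection, n=39, 30% |
|---|---|---|---|---|---|---|
| 2% | 0.945 | 0.057 | 0.957 | 0.048 | 0.057 | 0.052 |
| 5% | 0.870 | 0.081 | 0.906 | 0.053 | 0.068 | 0.054 |
| 10% | 0.764 | 0.163 | 0.820 | 0.084 | 0.106 | 0.059 |
| 18.4% | 0.628 | 0.398 | 0.701 | 0.164 | 0.217 | 0.091 |

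Changing the later hazard (n=78, 50% response, 5,000 trials) gives rejection of 0.057 / 0.091 / 0.226 / 0.520 at 0.01 per month and 0.058 / 0.075 / 0.140 / 0.338 at 0.04 per month, in the same order of early death.

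**Step 3: landmark at month 3, status also fixed at month 3.** HR is 0.993 to 1.013 and rejection 0.048 to 0.061. Leaving early deaths unclassified, with time still counted from treatment, gives the same log-rank result.

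**Step 4: where the landmark must sit.** Section 6.3 states "Subjects must be evaluated at the Clinical Center at the 1 month (+/- 7 days) and 3 month" visits, the latter also with a 7-day window. From then, 6.4 schedules "Complete blood counts with differential (every other week +/- 3 days"). A 3-month visit 7 days late, confirmed at the next count, settles status 7 + 14 + 3 = 24 days after month 3, or 0.79 month.
- Status fixed 24 days after month 3: a 3-month landmark leaves HR 0.947 to 0.973. A 4-month landmark gives HR 0.994 to 1.009 and rejection 0.049 to 0.060.
- Status fixed at 5 months (2-month duration counted from month 3), n=78: a 3-month landmark leaves HR 0.889 to 0.895 at 50% response and 0.924 to 0.934 at 30%. A 5-month landmark gives HR 0.997 to 1.015 and rejection 0.050 to 0.055.

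**Step 5: transformation-free survival.** Death is one of its events, so the early-event share cannot be lower than the early-death share.

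**The case against.** **The plan already warns of bias, and the comparison is exploratory.** True, and this limits the severity. A warning still does not correct a distortion that a standard method removes.

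**The plan never says early deaths are non-responders.** Also true, and the bias from this source vanishes if they are left unclassified. The supporting text is indirect: the 8.3 denominator belongs to the primary test, and the Appendix B entry refers to deaths during treatment, while dosing lasts about 11 days (5.1). Counting them as non-responders remains the natural reading, and silence leaves open a choice that changes the result.

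**The effect is small unless early mortality is high.** This stands: rejection is 5% to 8% at 2% to 5% early death. The 18.4% comes from h-ATG/CsA, with 3 of the 7 deaths attributed to h-ATG, and this trial excludes life expectancy under 6 months (4.2.11).

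**The log-rank test at 5% and full follow-up are not in the plan.** Correct; they are assumptions used to size the bias. The shift in the hazard ratio does not depend on the choice of test.

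**Confirmation could be complete by month 3**, since counts are weekly until then. If so, a 3-month landmark would serve. Conversely, if 6- or 12-month responses also define a responder, a fixed 4-month landmark would place later responders with the non-responders, and a time-dependent covariate is the better choice.

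**Conclusion.** The concern holds. As written, both survival comparisons start before response can be known, and the plan gives no method to deal with that. Provided early deaths are counted as non-responders, responders are favoured by construction. The bias is small at 2% to 5% early mortality (null HR 0.87 to 0.96 at n=78 with status fixed at month 3) and material at 10% or more (HR 0.82 or lower). These figures rest on assumed early mortality, a constant later hazard and complete follow-up. A landmark placed when status is settled returns the HR to about 1.0 and rejection to 5% to 6%; one placed earlier leaves part of the bias.

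A landmark does not make the groups prognostically comparable. Nor does it repair survival and marrow follow-up of non-responders after they leave the study, which the plan does not specify.

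**What to change.** In 8.2.2 and 8.2.4, replace the comparison from treatment with a landmark analysis:
- Include subjects alive at the landmark, group them by response status at that time, and count time from there. For transformation-free survival, also require no recorded event by then; no marrow is scheduled between baseline and 6 months, so unrecorded progression is possible.
- Set the landmark when status is settled: 4 months after first dose for confirmed 3-month response, or about 5 months if the 2-month duration is required from month 3. Alternatively, fit response as a time-dependent covariate, particularly if later responses count.
- State how deaths before the landmark are handled, and keep them in whole-cohort overall survival.
- Retain the existing caution.
- Separately, because follow-up has ended (10.4), use whatever vital status and transformation data exist for off-study subjects, and report the follow-up achieved in each group and its limits.

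The cost is analysis wording, with no new visits. Early deaths leave the landmark comparison: in the simulation at n=78, about 2 to 14 of 54 to 58 deaths at 3 months, 3 to 16 at 4 months and 5 to 17 at 5 months.
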